## **Protocol Title: Trial to Improve Multisensory Neural Processing, Language & Motor Outcomes in Preterm Infants**

---

language intervention and that preterm infants exposed to STS care have increased multisensory processing efficiency compared to those who do not.

We have now designed a prospective, interventional RCT in preterm infants aimed at restoring more typical multisensory, rather than the unisensory, processing measures that were the outcomes of our pilot studies.

Our multisensory intervention using parents' voice and nurturing touch can be administered regularly in the NICU during sensitive periods of sensory development, even when parents cannot always be present. Our test of this multisensory intervention will involve 23 sessions of standardized, therapist-administered, auditory-tactile stimulation. This treatment will combine contingent presentation of recorded mother's voice delivered using a suck-activated system during holding with supportive tactile containment against the therapist's chest. This treatment will be tested in an internally-valid RCT. In addition to testing the efficacy of the treatment on gold-standard measures of language and motor functioning, we will also test whether the treatment effect is due to intermediate treatment effects on multisensory and unisensory processing. Understanding the mechanism by which the treatment works is important for laying the foundations of future improvements and potential recommendations for treatment that might be useful for wide-spread use even in lower resource settings with the ultimate goal of improving neurodevelopmental outcomes for these premature infants.

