### **Study procedures**

For infants who meet inclusion criteria at 31 weeks, consent is obtained and parent's voice is recorded and parent-scented T-shirt may be collected when possible. Study staff may approach parents of eligible infants about the study and obtain consent slightly before the infant is 31 weeks, however, other study procedures will not start until the infant reaches 31 weeks. Infants are then randomized to the control or intervention group. If a patient is randomized to the control group, parents will be given the opportunity to consent to the secondary part of the study if they are interested. This part of the study is observational only and does not influence randomization. ERP testing is performed prior to the intervention. Infants assigned to the MS group receive the standardized MS intervention over 2 weeks, starting at 32 0/7 weeks PMA or at enrollment prior to 36 weeks. For both control and intervention groups, standard care includes skin-to-skin care on parent, when present, and playing of parents' voice non-contingent on infant suck. Parents may be asked to complete the Baby Care Questionnaire (BCQ) during infant's stay in the NICU or as soon as possible after discharge. Prior to the infant's discharge, a brief neurological examination (HNNE) and motor assessment (GMA) may be completed. ERP is repeated after intervention is completed, which occurs at 36 weeks PMA on average.

All infants are seen at the NICU Follow-Up Program clinics at 3-4, 9-12 (Year 1) and 22-26 months (Year 2). At the 3-4 month visit, study staff may obtain the Baby Care Questionnaire (BCQ), a brief neurological exam (HINE), and a brief motor assessment (GMA). At the Year 1 visit, study staff may obtain the BCQ, Infant Toddler Sensory Profile (ITSP), HINE, GMA, Bayley III, and the Parenting Styles and Dimensions Questionnaire (PSDQ). At Year 2, study staff may obtain the the Bayley III, HINE, BCQ, CBCL, PSDQ, and PLS-5.

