##### *Exposure to recorded parent's voice:*

Preterm infants in the NICU currently receive noncontingent recorded parents' voice during two 20 minute sessions per day. Recordings are standardized. Recordings are then played through a sterilizable device (DINO-egg).

To enhance standard care, we will ensure that all parents have a voice recording before study start when possible so that the majority of infants are exposed to parent's voice. A standard therapist recording may be used when it is not possible to obtain parent's voice. Monitoring of standard care will be accomplished through bedside logs, designed to be filled out by nursing staff and family when DINO-egg is played.

*Skin-to-skin holding:* Per standard care, STS care will be carried out by parents in both groups. Parents in the NICU currently use either their hands or positioners to facilitate prolonged STS. Infants are placed in a prone position with head positioned over the sternum, allowing transmission of breath and heart sounds to the developing ear. Deeper pressure is applied to offer support and feedback to the child's bottom. Session length is set to a minimum of 45 minutes per unit protocols. When primary caregivers are not comfortable with direct skin-to-skin contact (e.g. are not a direct relation to the child, or parent or child skin problem), a thin single-use hospital gown that is not previously imprinted with the parent's scent is used to facilitate the experience without hindering sound transmission. In order to ensure safety during STS holding, vital signs including heart rate, breathing patterns and rate, oxygen saturation and temperature are continuously and automatically monitored with preset alarms per unit protocol. If any negative deviation from the infant's daily vital patterns occurs, the nurses examine the infant and decide whether to stop the STS.

To monitor STS, we will review the medical record for daily start time, duration and caregiver during STS. We may also leave a STS log at bedside for parents who provide frequent STS to

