### Multisensory Intervention

*Rational:* Studies have shown that infant acquisition of early speech sound differentiation in term and preterm infants is essential to the construction of more complex cortical functions such as receptive language development. Furthermore, learning of language in infants is improved when language exposure is presented contingent on infant action and promptly after the action. Therefore, we will use preterm infants' active non-nutritive sucking as the behavior that activates an audio recording of mother's voice within a one second after the suck. The mother's voice provides auditory input, which purportedly contributes to the infants' representation of initial speech sound categories.

The mother's voice is a preferred stimulus and its frequency and patterns are distinguished early in life from other sounds.

The infant must repeat the action every ten seconds to continue to receive the positive reinforcement of mother's voice. This approach enables contingent linguistic input by the infant's mother's voice without parent having to be present. Because infant uptake of linguistic input may be enhanced during periods of calm attention to the auditory stimulus, the contingent linguistic input will be provided while the infant is in a state of autonomic stability. Thus, we will present the suck-contingent playing of parents' voice while skin-to-skin (STS) holding occurs. STS holding is a form of MS stimulation combining tactile, vestibular, olfactory and auditory input that has been demonstrated to improve autonomic nervous system stability. Although STS can induce deep sleep, the contingent presentation of parent's voice will be provided at the beginning of STS containment, when past work indicates that infants are still awake.

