*MS intervention protocol:* The MS intervention will be carried out in addition to standard care and will include two components: holding and light pressure containment of the infant against the cotton T-shirt covered chest of the therapist for tactile and non-specific auditory stimulation **simultaneous with** playing of mother's voice contingent on infant pacifier sucking for during a study session of no more than 15 minutes duration. No more than one study session will be completed per care period for each subject. Additionally, when possible, a 100% cotton T-shirt square scented with parent's skin may be placed within 2 cm of infant's face on the therapists' chest, to provide olfactory stimulation without risk of suffocation. The 12-23 intervention sessions will be dispersed across 2-3 weeks.

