## Protocol Title: Trial to Improve Multisensory Neural Processing, Language & Motor Outcomes in Preterm Infants

---

When the dependent variable is continuous, we will use ANOVAs when controlling for pretreatment variables and independent sample t-tests when there is no need for a covariate. When testing the nominal form of the sensory reactivity and adaptation outcome, we will use logistic regression.

*Statistical power:* Using PASS software, the estimated power using a 1-tailed test for an effect size based on the pilot data (Hedges  $g = .74$ ) with a sample size of 180 is over 99%. Even if the actual effect size is  $g = .35$ , we will have over 80% power to detect the effect under the proposed conditions. Detecting the required minimum effect size is probably for a number of reasons.

First, the expected effect size for the proposed treatment on multisensory processing should be larger than that derived from the pilot because the treatment used in the pilot

(i.e., skin-to-skin contact *without* the suck-contingent presentation of parent's voice) and theory strongly suggests the multisensory treatment will produce a larger effect than a unisensory treatment. Secondly, a medium main effect size of the proposed treatment on neurodevelopmental outcomes is expected because multisensory processing is moderately to strongly associated with later neurodevelopmental outcomes.

*Our second aim is to test the role of multisensory responses at discharge in mediating intervention effects on later sensory adaptation, and motor and language outcomes.*

Mediation models are presented in Figure 3. The indirect effect (the product of the a path coefficient \* the b path coefficient) will be tested for significance using the bias-corrected bootstrap method. The a path is the main effect of treatment on the ERP measure of multisensory processing. The b path is the association of the ERP measure of multisensory processing with the outcome controlling for the treatment group.

[figure not shown]

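### Aim 1 power: the claim that the effect should exceed the pilot g = .74 is not supported for the contrast this trial randomises, and the fallback g = .35 gives about 76% power at 180, not over 80%

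*Combined protocol and SAP*

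**What the plan says.** The Aim 1 paragraph on statistical power (Statistical Analysis) reports "the estimated power using a 1-tailed test for an effect size based on the pilot data", Hedges g = .74, as over 99% with 180 infants. It adds that g = .35 would still give over 80%. It then argues that the minimum effect will probably be detected. The first reason is that "the expected effect size for the proposed treatment on multisensory processing should be larger than that derived from the pilot", since the pilot used skin-to-skin contact without suck-contingent voice and theory favours a multisensory over a unisensory treatment.

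Other sections bear on that reason:

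- Background and rationale, on the pilot work: "preterm infants exposed to STS care have increased multisensory processing efficiency compared to those who do not".
- Study procedures: "For both control and intervention groups, standard care includes skin-to-skin care on parent, when present", together with non-contingent playing of the parents' voice.
- Standard Care, on parental skin-to-skin: "Session length is set to a minimum of 45 minutes per unit protocols".
- Multisensory Intervention, on the added treatment: "holding and light pressure containment of the infant against the cotton T-shirt covered chest of the therapist", with contingent voice, in sessions of at most 15 minutes.
- Multisensory Intervention, rationale: "STS holding is a form of MS stimulation combining tactile, vestibular, olfactory and auditory input".
- Aim 2 power: recalls that a medium effect on multisensory processing was expected under Aim 1.

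**The concern.** For the new effect to exceed the pilot effect by the stated reasoning, the randomised contrast would have to be the pilot contrast with something added. The comparator, the form of holding and the multisensory label all appear to differ. If so, g = .74 is not an estimate for this trial, and the first reason offered for reaching the minimum effect falls away.

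What is at stake is how the result is read. A null finding on the primary outcome would be judged against a stated power of over 99%, and the Aim 2 a path takes its expected size from the same argument.

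**Working it through.** **Inputs.** Pilot g = .74, fallback g = .35, a one-tailed test and 180 analysed (90 per arm) come from the Aim 1 power paragraph. Recruitment of 230 (115 per arm) and 10% attrition come from Power/Sample Size. Alpha is not stated there; one-sided .05 is assumed. No effect size is given for the contrast actually randomised.

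**1. Reproduce the plan's figure.** With n per arm, power = P(T > t[.95, 2n − 2]), where T is noncentral t with noncentrality g × √(n/2). For g = .74 and n = 90 the noncentrality is .74 × √45 = 4.96 and power is 99.95% (99.85% at two-sided .05). The stated figure reproduces, so the question concerns the input.

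**2. Compare the two contrasts.**

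| | Pilot, as described | This trial |
|---|---|---|
| Comparator | Infants without skin-to-skin | Standard care: parental skin-to-skin when a parent is present, plus non-contingent recorded voice |
| Treatment | Skin-to-skin, no contingent voice | The same standard care, plus a hold against a therapist's T-shirt with contingent voice, at most 15 minutes |
| Label | Unisensory (Aim 1 power) | Multisensory; but the intervention rationale also calls skin-to-skin multisensory |

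The pilot contrast is not nested in the new one, and the multisensory-versus-unisensory reason conflicts with the document's own description of skin-to-skin.

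**3. How far over 99% holds.** At 90 per arm, power is at least 99% for g ≥ .594, and .594/.74 = 80% of the pilot value. Power is at least 80% for g ≥ .372.

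**4. Check the fallback.** For g = .35 and n = 90 the noncentrality is .35 × √45 = 2.35 and power is 75.6% (75.9% by the normal approximation). This is not over 80%. But 230 × 0.9 = 207, while 180 = 200 × 0.9, the size before the increase reported under Inclusion and Exclusion Criteria. At 207 (103.5 per arm) the noncentrality is .35 × √51.75 = 2.52 and power is 80.6%. At two-sided .05 the figures are 64.6% and 70.8%.

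**5. Covariate gain.** The plan will adjust for pretreatment ERP but states no correlation r with the outcome. Adjustment makes g act like g/√(1 − r²). To reach .372 from .35 at 180, r must be about .34: .35/√(1 − .34²) = .372. If r were .5 (assumed), power at 180 would be about 86%.

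**6. Sensitivity** (one-sided .05, unadjusted; every g other than .74 and .35 is an assumption):

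| g | Power at 180 | Power at 207 |
|---|---|---|
| .74 | 99.95% | 99.99% |
| .60 | 99.1% | 99.6% |
| .50 | 95.5% | 97.4% |
| .37 (half the pilot) | 79.6% | 84.3% |
| .35 | 75.6% | 80.6% |
| .30 | 64.1% | 69.4% |
| .25 | 51.0% | 55.9% |
| .20 | 37.9% | 41.7% |

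**7. Link to Aim 2.** Aim 2 power assumes an a path of at least 0.26 (6.8% of variance). With equal arms r = g/√(g² + 4), so 0.26 corresponds to g = 2 × .26/√(1 − .26²) = .54. The fallback g = .35 corresponds to .35/√(.35² + 4) = 0.17, about 3% of variance. The Aim 1 minimum effect therefore does not meet the Aim 2 assumption. Moreover, the Aim 1 paragraph uses the word medium for the effect on neurodevelopmental outcomes. For multisensory processing it claims more than the pilot.

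**The case against.** The plan does not rest on .74 alone. Power/Sample Size admits that pilot estimates have wide confidence intervals and for that reason also gives the lowest effect the sample affords. The over-99% figure is tied expressly to the pilot effect and is correct on that condition. Both points stand. They limit the criticism to the justification and to the fallback's figure, which misses its stated power at 180.

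The comparator behind g = .74 is not named in the power paragraph. Reading it as skin-to-skin versus none depends on the Background description, which does not attach the number to that contrast. This also stands, and it is why the point says only that the contrast appears to differ.

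A reader might infer that the true effect must be below .74, or that the trial is underpowered. The documents support neither inference. Contingent voice is a new component; Aim 3 cites g = 1.06 for it, although on speech processing. The intervention section calls a parent's presence a rare occasion, so skin-to-skin in the control arm may be sparse. Clothing is not a clean distinction either, since standard care allows a thin gown in some cases. Nor does comparing minutes of holding settle anything: the added hold totals at most 12 × 15 = 180 to 23 × 15 = 345 minutes, but neither the pilot dose nor the number of parental sessions is given.

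Finally, the unadjusted figures ignore the planned covariate. That is fair, but the plan quantifies no gain from it.

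**Conclusion.** The concern holds as a fault in the justification. The statement that the effect should exceed the pilot is unsupported and, in its multisensory-versus-unisensory reason, contradicted by the plan's own text. Over 99% is right only conditionally: it needs g of about .59 or more at 180, and no source is given for such a value in the randomised contrast.

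The plan's own minimum effect, g = .35, gives about 76% at 180 and about 81% at 207. These figures assume one-sided .05, equal arms and no covariate gain. The documents leave open whether the true effect is above or below the pilot value. This is an inexpensive correction to a stated power argument and does not show that the sample size is wrong.

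**What to change.** 1. Delete the sentence that the effect should be larger than the pilot's, with its multisensory-versus-unisensory reason.
2. Keep g = .74 and over 99% only as a figure conditional on the pilot effect. Name the pilot's comparator and say that its contrast differs from this trial's.
3. Base Aim 1 power on g = .35: about 76% at 180 and about 81% at 207, unadjusted. State alpha, and correct the after-attrition number (230 less 10% is 207).
4. If a gain from the pretreatment ERP covariate is claimed, state the assumed correlation.
5. Add a short range of smaller effects for the actual contrast, labelled as assumptions.
6. Make the expected effect on multisensory processing agree between Aims 1 and 2, and carry the result into Aim 3 where it relies on the Aim 2 power analysis.

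Cost: a rewritten power section and a less favourable headline figure. Conduct and sample size stay as they are.

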*Covariates:* Biological variables are factored into our research design as potential covariates. Several pretreatment covariates will be statistically controlled if needed. These variables will be quantified at the pretreatment period, as past research or theory suggests they may be associated with neurodevelopmental outcomes or sensory processing. If preliminary tests of between-group differences of these pretreatment variables and the pretreatment variables showing between-group differences are associated with putative mediators or neurodevelopmental outcomes, these will be statistical controlled. Their statistical interaction with treatment group must be tested as part of the process of determining whether they should be statistically controlled. Thus, the possibility that treatment varies as a function of these biological variables will also be explored. These include: gestational age at birth, sex, presence of severe white neural injury on neuroimaging (intraventricular hemorrhage grade III or IV, periventricular leukomalacia, cerebellar hemorrhage, ischemic or thrombotic injury), presence of systemic inflammatory conditions (history of necrotizing enterocolitis Bells Stage

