## **Protocol Title: Trial to Improve Multisensory Neural Processing, Language & Motor Outcomes in Preterm Infants**

---

IIA or above, culture documented sepsis or meningitis, moderate or severe bronchopulmonary dysplasia per modified Shennan definition), cumulative caffeine exposure post intervention, total parental skin-to-skin time during the study period and pretreatment status on the General Movements Assessment (GMA).

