### **Analysis Plan**

#### **Power/Sample Size**

A total sample size of 230 (115 in each group) will be recruited. Although attrition in past similar work has been much lower, we estimate power under an assumption of 10% attrition (i.e., 180). Because pilot studies afford effect size estimates with wide confidence intervals due to small sample sizes, power analysis results were conducted for the effect size available from pilot data and lowest effect size that the after-attrition sample size affords. Feasibility of the expected effect size is then evaluated. Power analyses are based on primary variables (multi- and uni- sensory processing). If between-group differences occur on the putative covariates (i.e., pretreatment variables related to the outcomes) and they are associated with putative mediators or outcomes, the pretreatment variables will be statistically controlled after ensuring that the homogeneity of slopes assumption has been met. Pretreatment ERP variables will be statistically controlled regardless of the effect size of between-group differences to improve effect size estimates. Missing data will be handled using multiple imputation.

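### As written, the Aim 2 and 3 mediation models adjust for severity covariates only when the arms differ on them, which is the wrong trigger for the ERP-outcome path

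*Combined protocol and SAP*

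**What the plan says.** The Statistical Analysis section tests an indirect effect, the product of the a path (treatment on ERP) and the b path, with a bias-corrected bootstrap. It defines the second factor: "The b path is the association of the ERP measure of multisensory processing with the outcome controlling for the treatment group". It points to Figure 3 for the models, and that figure is not visible. Aim 3 uses the same procedure with unisensory mediators (speech processing for language, touch processing for motor).

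Covariates are dealt with elsewhere. Under Power/Sample Size, one group is unconditional: "Pretreatment ERP variables will be statistically controlled regardless of the effect size of between-group differences to improve effect size estimates". The rest are conditional. That rule opens "If between-group differences occur on the putative covariates (i.e., pretreatment variables related to the outcomes"), also requires an association with a mediator or outcome, and adds a homogeneity-of-slopes check. The Covariates paragraph under Randomization sets the same double condition and begins from testing: "If preliminary tests of between-group differences of these pretreatment variables". Both places name putative mediators, so as written the rule governs the mediation models as well as the group comparisons. Neither gives a threshold.

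The Covariates paragraph explains that the variables were chosen because "past research or theory suggests they may be associated with neurodevelopmental outcomes or sensory processing". They include gestational age at birth, sex, severe brain injury and systemic inflammatory conditions. The visible text does not ask for b-path adjustment irrespective of arm balance, or for a sensitivity analysis for mediator-outcome confounding.

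**The concern.** Randomisation protects the a path and the total effect. It does not protect the b path, because nobody assigns an infant's ERP. A variable confounds the b path if it influences both ERP and later development. Whether the two arms happen to differ on it is irrelevant to that. Under randomisation the arms differ only by chance, so chance decides whether a real confounder is adjusted.

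The plan's own reason for listing these variables makes them candidate common causes. If treatment shifts the ERP, and sicker infants have both less typical ERPs and lower scores, the analysis can report mediation when the ERP has no effect on development. Mediation by the multisensory response is a stated secondary objective in the Study Summary.

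**Working it through.** **1. The plan's own figure.** Inputs from the Aim 2 power paragraph: a = b = .26, bias-corrected bootstrap. The documents give no level for Aim 2, so a two-sided 95% interval is assumed. With no confounder in the model, simulated power is .90 at N=180 (plan: over 80%, reproduced) and about .83 at N=148 (plan: 80%, slightly conservative).

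**2. Spurious b when the true b is zero.** Let one severity factor correlate r_pre with pretreatment ERP, r_post with post-treatment ERP and r_Y with outcome, and let rho be the pre-post ERP correlation, all within arm. With treatment and pretreatment ERP adjusted and severity omitted:

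b = r_Y × (r_post − rho × r_pre) / (1 − rho²)

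This is zero only if r_post = rho × r_pre. With rho = .5 and all severity correlations equal to r:
- r=.2: .2 × (.2 − .1)/.75 = .03
- r=.3: .3 × (.3 − .15)/.75 = .06
- r=.4: .4 × (.4 − .2)/.75 = .11

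**3. False-positive indirect effects.** From the plan: 90 per arm (its post-attrition 180) and a treatment shift on ERP of g = .35 or .74 (Aim 1 power text). Assumed: all correlations, and a gate requiring an arm difference plus a p<.05 association with post-treatment ERP or outcome. There were 2,000 trials per cell with 500 bootstrap draws each (standard error at most 1.1 points). Simulated mean b agreed with the formula within .005 in every cell. Ranges cover both values of g.

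| Assumed case | Formula b at r=.4 | Error, r=.3 | Error, r=.4 |
|---|---|---|---|
| Base: rho=.5, gate p<.05 | .11 | 13% | 26-29% |
| rho=.7 | .4 × (.4 − .28)/.51 = .09 | 9-13% | 17-19% |
| rho=.3 | .4 × (.4 − .12)/.91 = .12 | 15-18% | 31-41% |
| Severity half as strong after as before | .4 × (.2 − .2)/.75 = 0 | 6-8% | 6-8% |
| Severity half as strong before as after | .4 × (.4 − .1)/.75 = .16 | 19-21% | 43-46% |
| Base, gate absolute d above .1 | | 10% | 18% |
| Base, gate absolute d above .2 | | 12% | 24-26% |

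Reference cells: no confounding 7-8% (the bootstrap's own floor); r=.2, 8-9%; no treatment effect on ERP with r=.4, 2%. Smaller base-case repeats (300 to 800 trials) gave 14-15% at r=.3 and 23-29% at r=.4. One 500-trial repeat gave 11% at r=.3, within sampling error of the main figure.

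A differently scaled model, with direct severity loadings of .2, .3 and .4 on ERP and outcome, gave 14%, 34% and 70%, against 7-8% when severity was adjusted. It supports the direction but not a particular size. In that model, with true b = .26 (true indirect effect .26 × .26 = .068), the plan's rule estimated .080, .096 and .119.

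**4. How often the gate opens.** A single severity variable entered in 4-6% of trials under the p<.05 gate and in about 50% under absolute d above .1. With five proxies screened at p<.05, at least one entered in 10-19% of trials, which barely changed the error rate.

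**5. What adjustment buys.** Adjusting for the exact severity variable gave 6-9% in every cell with a treatment effect on ERP. Real covariates are proxies. If they explain a share R² of severity and all severity correlations equal r, the remaining spurious b is r²(1 − R²)/(1 + rho − 2r²R²). At r=.4 and rho=.5:
- R²=0: .16/1.5 = .11
- R²=.3: .112/1.404 = .08
- R²=.5: .08/1.34 = .06

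Simulation with five proxies at r=.4 left 21% error at R²=.3 and 10-13% at R²=.5. At r=.3 it left 13% and 9%, against 14-16% under the plan's rule in the same runs.

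**6. Level or change.** Table 1 defines the amplitude variable as a pre-post change. With pretreatment ERP in the model, change and post-treatment level give the same b, since post = change + pre. A change score without pretreatment ERP gives b = r_Y(r_post − r_pre)/(2 − 2rho), which is zero only if severity acts equally before and after. At r=.4, rho=.5 and severity half as strong after, b = .4 × (−.2)/1 = −.08, with 17-23% error.

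**The case against.** Several points on the other side stand.

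- **The models may be in Figure 3.** It is not visible and could show covariates. The gate also sits under Power/Sample Size, with slope-homogeneity language suited to group comparisons. The point is therefore limited to the visible text. But that text names mediators twice, and a figure showing more would have to be reconciled with it.
- **Pretreatment ERP already absorbs some severity.** True. It removes the bias entirely only when r_post = rho × r_pre, and the documents give no reason to expect that. The exclusion criteria may also narrow the severity range.
- **Every correlation is assumed, and the gate has no stated threshold.** True. The cells run from no excess to 46%. The nominal Infant Toddler Sensory Profile outcome was not simulated.
- **The remedy looks better than it is if the simulation adjusts for the very variable that creates the bias.** True. A reader might infer that a fixed covariate set restores the error rate to its floor. That needs near-complete measurement of severity, and several of the plan's covariates are diagnoses recorded as present or absent.
- **The 4-6% entry rate describes one covariate.** A reader might infer that the plan omits adjustment in about 95% of trials. The plan screens a list, so that does not follow.

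None of this makes arm imbalance a valid criterion for b-path adjustment.

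**Conclusion.** The point holds for the plan as written in the Covariates paragraph and Power/Sample Size: gating on arm differences is wrong for the b path and can bias the Aim 2 and 3 indirect effects. Its existence is clear from the rule, but its size is not. In the base case the error is about 13-15% at r=.3 and 23-29% at r=.4, against a 7-8% floor. There is no meaningful excess at r=.2, when severity is half as strong after as before, or when treatment does not move the ERP.

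A reader might infer that any mediation finding from this trial would be spurious. The documents do not support that, because they give no severity correlations. Nor does the point touch Aim 1, including the primary multisensory response, which is a randomised comparison. Aim 3 is described as exploratory. This should be fixed before the mediation analysis is run; confidence is moderate because the magnitude rests on assumed inputs.

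**What to change.** For Aims 2 and 3, state that both the mediator model and the outcome model contain treatment, pretreatment ERP and a fixed set from the plan's own list, whatever the arm balance: gestational age at birth, sex, severe brain injury known before randomisation, and inflammatory conditions with documented onset before randomisation. State whether the mediator is the post-treatment level or the pre-post change.

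Three listed variables need care. The Covariates paragraph says "These variables will be quantified at the pretreatment period", yet the list includes "cumulative caffeine exposure post intervention, total parental skin-to-skin time during the study period". Neither can be known before treatment, so they should not be added automatically. The list also has "pretreatment status on the General Movements Assessment (GMA"), but the only NICU assessment of that kind under Study Procedures is before discharge. Include it only if it was measured before treatment.

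Because adjustment reduces the confounding without removing it, add one sensitivity analysis: how large a residual mediator-outcome error correlation would bring the indirect effect to zero.

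The cost is SAP wording, a few degrees of freedom, and work to date diagnoses from the medical record, since the documents do not show that onset dates are collected. The adjusted b path may also be smaller than the zero-order correlations of 0.41-0.42 cited in planning, so power for the indirect effect may be lower than stated.
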